1 PROTOCOL SUMMARY

1.1 SYNOPSIS

Title: Evaluating Design Improvements with SONNET 3 (EAS) in Experienced Cochlear Implant Users

Study Description: This prospective IDE study will use a single-arm, repeated measures design with subjects serving as their own control. Participants will be experienced cochlear implant (CI) users wearing an approved MED-EL audio processor. The study will demonstrate patient-reported improvement in processor design, usability, and satisfaction with the SONNET 3 (EAS) (EAS) Audio Processor compared to their existing audio processor. Participants will complete a take-home trial with the SONNET 3 (EAS). At Visit 2, participants will complete a custom questionnaire comparing design and usability with SONNET 3 (EAS) (EAS) to their existing audio processor.

Objectives: Primary Objective: To demonstrate patient-reported improvement in processor design with the SONNET 3 (EAS) (EAS) audio processor compared to the existing audio processor.

Secondary Objectives: To compare user experience with the SONNET 3 (EAS) (EAS) audio processor to the existing audio processor.

Endpoints: Primary Endpoint: At least 77% of participants will report improvement (mean score >3 on a 6-point Likert scale) in processor design with the SONNET 3 (EAS) (EAS) compared to the existing audio processor on the Design subsection of the Audio Processor Comparison Survey (APCS) at Visit 2.

Secondary Endpoints:

1. Summary of patient-reported satisfaction ratings on subsections of the Audio Processor Comparison Survey (APCS) with SONNET 3 (EAS) (EAS) at Visit 2.
2. Summary of audiologist-reported satisfaction ratings on subsections of the Audiologist Survey at enrollment conclusion.

Study Population: This study will include 20 experienced MED-EL CI users who are consistently wearing a SONNET (EAS) or SONNET 2 (EAS) audio processor at ≥12 months post-activation and are able to complete the study procedures.

Description of Sites

One (1) US academic medical center will enroll participants

Enrolling Participants:

Participants will be experienced MED-EL CI recipients using the

commercially available SONNET (EAS) or SONNET 2 (EAS) audio processor (MED-EL Elektromedizinische Geräte GmbH, Innsbruck, Austria). For the experimental procedure, participants will be fit with a SONNET 3 (EAS) (EAS) audio processor (MED-EL Elektromedizinische Geräte GmbH, Innsbruck, Austria). The SONNET 3 (EAS) (EAS) audio processor is an external component and is indicated for use on

Description of Study

Device:

patients who have been implanted with a MED-EL cochlear implant. The SONNET 3 (EAS) (EAS) audio processor consists of the control unit, coil, coil cable, microphone cover, earhook, and battery pack. SONNET 3 (EAS) (EAS) is programmed with the MAESTRO 11.0 or higher Fitting Software (MED-EL Elektromedizinische Geräte GmbH, Innsbruck, Austria).

Study Duration: Enrollment is expected to take 12 months, and participant follow-up will last up to 1 month. The estimated time from the first subject's first visit to the last subject's last visit is 13 months.

Participant Duration: Each subject's participation will last approximately 1 month from enrollment to the final study visit.

1.2 SCHEMATIC OF STUDY DESIGN

Visit 1: Enrollment

- Informed consent or assent (if required)
- Parental permission (if applicable)
- Participant leaves with SONNET 3
- **See Study Schedule (Section 7.2) and Schedule of Events Table (Section 7.2.5) for more detail**

Visit 2: 3-Week Follow Up

- Audio Processor Comparison Survey completed by participant
- **See Study Schedule (Section 7.2) and Schedule of Events Table (Section 7.2.5) for more detail**

Enrollment Conclusion

- Audiologist Survey completed by study team
- **See Study Schedule (Section 7.2) and Schedule of Events Table (Section 7.2.5) for more detail**

2 INTRODUCTION

2.1 STUDY RATIONALE

Cochlear implant audio processors capture and deliver acoustic signals to the internal device. They accomplish this through dual-microphone technology and signal processing algorithms developed to preferentially detect and enhance speech signals relative to background noise. The audio processor is worn all waking hours, every day for best outcomes. The requirements of a reliable audio processor are two-fold; reliable performance of signal processing and front-end microphone features ensures clear speech, while a comfortable design reduces barriers to wearing the device all waking hours.

Manufacturers of cochlear implants release periodic updates to processor design to enhance usability and the listening experience. Insurance companies in the United States are typically contracted to subsidize the purchase of new processors every 5 years, depending on the coverage plan and the region. However, insurance providers may deny coverage for new processors without data to support the efficacy of new technology compared to previous processor designs.

2.2 BACKGROUND

The SONNET 3 (EAS) audio processor (AP) is MED-EL's latest BTE design (Innsbruck, Austria) and improves upon the existing SONNET/SONNET 2 (EAS) APs with enhanced physical design and Bluetooth useability. The SONNET 3 (EAS) is programmed with MAESTRO 11 software, both of which have been submitted to the FDA for approval in June 2024 (refer to submission P000025/S131). MAESTRO 11 includes minor improvements in the user interface (see section 6.1.3). The SONNET 3 (EAS) offers a smaller and lighter design for better wearing comfort on the ear (see section 6.1.3). New earhook options, including a large earhook and a flexible silicone earhook designed for improved flexibility on the pinna, allow the recipient to further customize their wearing options. Bluetooth streaming in the SONNET 3 (EAS) is simplified with an integrated 2.4GHz receiver that no longer needs an intermediary device to stream music, phone calls, and other audio from smart devices. These design changes are an answer to the field's request for lighter wearing options with integrated streaming capabilities.

In 2012, Lorens and colleagues compared subjective benefit of a new audio processor (AP) design in a group of 10 experienced electro-acoustic stimulation (EAS) CI recipients who were utilizing the MED-EL DUET AP. Subjects were upgraded to the DUET 2 AP and completed a custom questionnaire at three intervals during a 3-month trial to study the effects of user preference over time. The custom survey compared aspects of user-perceived listening ability and wearing comfort with DUET 2 to the DUET AP. Subjects' preference for the sound quality of speech with DUET 2 improved at each interval, achieving 34% preference over the DUET AP by the 3-month interval. Overall, 70% of subjects were either very satisfied or satisfied with the

wearing comfort of the DUET 2, and no subject was dissatisfied with the wearing comfort of the DUET 2. Results suggest that experience with a new processor is important when measuring subjective impressions of these changes in AP design. The authors concluded that conversion from the old to the new AP model greatly improved patient satisfaction.

In 2015, Martin et al. gathered data from both implant recipients and professionals on the ease of use of the new Naída CI Q70 (Naída CI) AP from Advanced Bionics, and on the usefulness of the new functions and features available. Existing CI users who had recently upgraded to Naida CI answered a 25-question custom survey which included a section directly comparing the user's previous AP to the Naida CI AP. Feedback from professionals was captured through a 30-question survey probing their impressions on usability and fitting. In total, 186 subjects across 10 countries, and 23 professionals across 11 sites responded to the survey. The Naida CI was rated as similar or better than the previous AP models by more than 79% of the subjects for all areas. The new design of the Naida CI was rated as being better by 83% of subjects. Professionals ranked the Naida CI processor first in design compared to other previous models. Overall results showed high satisfaction with the new AP from users of all ages and experience levels, as well as from professionals.

Warren et al., 2019 compared subjective impressions of experienced Cochlear brand Nucleus 5 and Nucleus 6 AP users who trialed the Nucleus 7 AP. Comparative satisfaction with self-reported hearing ability and usability with the new AP was captured via a custom survey after 3 months using the device. The majority of subjects reported improvement in perceived hearing ability and device usability with the new AP design compared to their existing audio processor, with an average of 83% of participants (n=35) responding positively (>50 on a 100-point scale) to questions comparing features of the new AP to the existing model. The authors conclude that the assessment of effectiveness of ergonomic improvements in AP design are best captured through subjective evaluation after providing the user with adequate time and experience with the device to assess the comparative benefits to their previous device.

The purpose of this study is to evaluate patient-reported improvement in design and comfort with SONNET 3 (EAS) over the existing AP models available, and to measure patient-reported impressions of usability and satisfaction with the SONNET 3 (EAS) AP.

2.3 RISK/BENEFIT ASSESSMENT

2.3.1 KNOWN POTENTIAL RISKS

Any cochlear implant processor poses a risk of skin irritation or sensitivity to the processor materials. Materials in the SONNET 3 (EAS) (EAS) Audio Processor do not differ from those in the FDA-approved SONNET/SONNET 2 (EAS) Audio Processors. MED-EL has performed biological safety and compatibility testing with materials in the SONNET 3 (EAS) (EAS), and subjects with a skin or scalp condition that would preclude use of the audio processor will be excluded from this study. All cochlear implant processors and fitting software also pose a risk of overstimulation

and exposure to unwanted or uncomfortable sounds. The processor can be removed from the head at any time to immediately stop stimulation.

There is a remote chance that technical failure or suboptimal fitting of any audio processor leads to unwanted sensations, missing information, suboptimal hearing, or lack of benefit. Study participants who wish to stop using the SONNET 3 (EAS) (EAS) Audio Processor before study completion may withdraw from the study at any time and continue using their existing audio processor. Participants who experience poorer sound quality or performance with SONNET 3 (EAS) (EAS) may be reprogrammed after testing at Visit 2.

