5.4 PARTICIPANT WITHDRAWAL OR TERMINATION

5.4.1 REASONS FOR WITHDRAWAL OR TERMINATION

Participants or their parents/legal guardians may choose to withdraw from the study at any point during participation. The site principal investigator may terminate an individual's participation in the study for reasons outlined below:

- Noncompliance with the study protocol
- Health concerns that prevent required follow-up procedures or interval visits

The site investigators should report participant withdrawals and terminations to study monitors as soon as possible. Subjects who withdraw prior to completion of Visit 2 will be required to return the SONNET 3 (EAS) Audio Processor to receive compensation for Visit 1. Participants who are considered lost-to-follow-up should also be reported to study monitors immediately. Every effort should be made to contact participants lost-to-follow-up and determine the reason for noncompliance. If the SONNET 3 (EAS) is not returned, the subject's clinical audiologist will be made aware so that efforts can be made to retrieve the study device at a clinical follow-up appointment.

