5.4.2 HANDLING OF PARTICIPANT WITHDRAWALS OR TERMINATION

Withdrawn participants will continue to be seen by their clinical audiologist for regular follow-up care, but no additional data will be collected. Participants who sign the informed consent/assent form but do not complete all study intervals may be replaced and will return any study equipment to the site. Baseline data collected on withdrawn subjects who are replaced will not be included in the modified intent-to-treat (mITT) or per population (PP) analysis datasets.

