10.2 SAMPLE SIZE

The sample size estimate is based on attaining adequate power to test the primary hypothesis that at least 77% of participants will report subjective improvement in audio processor design with SONNET 3 (EAS) over the existing processor based on a single survey. The hypothesis test is a one-sample, one-sided test of the proportion of participants reporting an average score of >3 on the Audio Processor Comparison Survey (APCS) compared to 77%, based on the clinical trial for the Cochlear Nucleus 7 audio processor, where an average of 77% of participants responded with greater than neutral agreement (>50 on a 100-point scale) on survey questions addressing satisfaction with improved comfort with the new audio processor. For the purpose of this sample size calculation, 77% will represent the desired participant response proportion.

A power analysis was conducted using a binomial two-proportion test with the package 'pwr' in R. Using a 95% confidence interval, a sample size of 20 participants would provide 85% probability of rejecting the null hypothesis (H_0 : 77%). Calculations are based on the following assumptions:

- Hypothesized proportion: H_0 : $p < 0.77$;
- Expected proportion: H_1 : $p \geq 0.77$
- Significance level = 0.05
- One-sided
- Effect size $h=0.36$

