10.3 ANALYSIS DATASETS

The intent-to-treat (ITT) population is defined as all enrolled participants including withdrawn participants who have been replaced. The modified ITT (mITT) population is defined as all participants who completed Visit 1 and Visit 2. The per protocol (PP) population is defined as participants who:

- Completed Visit 1 and Visit 2
- Were using the SONNET 3 (EAS) device consistently throughout the trial period
- Are free from major protocol deviations, including but not limited to:
 - Non-use of the SONNET 3 (EAS) during the trial
 - Missing test measures from one or more intervals
 - Evidence of not meeting inclusion/exclusion criteria after completion of study intervals

Analysis for the primary endpoint will be completed on the mITT and the PP populations.

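### The protocol does not separate stopping SONNET 3 from leaving the study, so people who stop may never be surveyed and may be replaced, which can bias the primary proportion upward

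*Combined protocol and SAP*

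**What the plan says.** Four sections bear on a participant who stops wearing SONNET 3 before Visit 2.

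- **2.3.1 (Known Potential Risks):** "Study participants who wish to stop using the SONNET 3 (EAS) (EAS) Audio Processor before study completion may withdraw from the study at any time". The only study route it mentions for such a person is withdrawal.
- **5.4.1:** the site principal investigator may terminate participation, and one listed reason is "Noncompliance with the study protocol". Stopping the device is not named.
- **5.4.2:** once a participant is withdrawn, data collection stops. Those who consent but "do not complete all study intervals may be replaced and will return any study equipment to the site". Baseline data from withdrawn participants who are replaced stay out of both mITT and PP.
- **10.3:** "Non-use of the SONNET 3 (EAS) during the trial" is a major deviation, listed only under the PP definition. mITT requires completion of Visits 1 and 2 and sets no condition on device use. ITT includes replaced participants, but the primary endpoint is analysed on mITT and PP only.

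The APCS is given only at Visit 2 (7.1.1, 7.2.3, 7.2.5). Section 10.4.5 plans no adherence or retention analysis.

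**The concern.** The same person can take either of two routes, and no rule says which applies. On one route they withdraw or are terminated, give no rating and may be replaced by someone else. On the other they stay, complete the APCS and count in mITT. Section 10.3 makes sense only if the second route is open, yet 2.3.1 mentions only the first.

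The primary endpoint is the participant's own opinion of the design. Someone who gives up the processor because of fit, weight or earhook is plausibly among the least favourable raters. The study is open-label and has one arm, so no comparison group offsets selective loss. With 20 analysed, very few lost ratings are needed to move the result.

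**Working it through.** **The plan's own figure.** Section 10.2 describes the test thus: "The hypothesis test is a one-sample, one-sided test of the proportion of participants". It states that "a sample size of 20 participants would provide 85% probability of rejecting the null hypothesis", with null proportion 0.77, one-sided alpha 0.05 and h = 0.36. The one-sample arcsine formula gives power = Φ(h√n − z₀.₉₅) = Φ(0.36 × 4.472 − 1.645) = Φ(−0.035) = 48.6%. The stated 85% is not reproduced. That is a separate matter and does not decide this point. Only n = 20, the null of 0.77 and alpha of 0.05 are used below.

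**The two routes side by side.**

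| | Leaves (2.3.1 or 5.4.1, then 5.4.2) | Stays (10.3) |
|---|---|---|
| Who decides | Participant (withdrawal) or investigator (termination) | Participant stays and is not terminated |
| APCS rating | None | Taken at Visit 2 |
| Place in the sample | May be replaced | Kept |
| mITT | Out | In |
| PP | Out | Out |

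**Pass mark.** The plan names neither an exact nor an approximate test, so the exact one-sided binomial is assumed. For n = 20 and p = 0.77:

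- P(X = 20) = 0.77²⁰ = 0.0054
- P(X = 19) = 20 × 0.77¹⁹ × 0.23 = 0.0321
- P(X = 18) = 190 × 0.77¹⁸ × 0.23² = 0.0910

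The p-values are therefore 0.005 for 20/20, 0.037 for 19/20 and 0.128 for 18/20. Success needs at least 19 of 20. A z-test with the null variance splits in the same place. Its standard error is √(0.77 × 0.23 / 20) = 0.0941. At 18/20, z = 0.13 / 0.0941 = 1.38 (p about 0.08). At 19/20, z = 0.18 / 0.0941 = 1.91 (p about 0.03).

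**One or two people.** Suppose two participants stop and would score 3 or below.

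- Kept and surveyed: the result cannot exceed 18/20, so it fails.
- Both replaced, one replacement favourable and 18 others favourable: 19/20, which passes.
- Both replaced, both replacements favourable and 18 others favourable: 20/20, which passes.

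One person can be enough. One unfavourable stopper plus one other unfavourable rater gives 18/20. Replacing the stopper with a favourable rater gives 19/20.

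**Chance of a false pass.** Assume that the true proportion over everyone is exactly 0.77, that a fraction d stop, and that all who stop would score 3 or below. If they are replaced, the proportion among completers is 0.77 / (1 − d).

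| d (assumed) | Completers' proportion | P(≥19/20), replaced | P(≥19/20), surveyed |
|---|---|---|---|
| 5% | 0.811 | 8.5% | 3.7% |
| 10% | 0.856 | 19.3% | 3.7% |
| 15% | 0.906 | 42.6% | 3.7% |
| 20% | 0.963 | 82.8% | 3.7% |

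The documents give no stopping rate. At d of 5% and 10%, the expected numbers of stoppers among 20 enrolled are 1 and 2.

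**The case against.** A reader might infer that 2.3.1 and 5.4.1 flatly contradict 10.3, or that the site alone decides who is surveyed. The text supports neither. Both 2.3.1 and 5.4.1 are permissive, and neither obliges a stopper to leave. The sections can be read together: a non-user who attends Visit 2 is in mITT and out of PP, and one who withdraws is in neither. Under 2.3.1 the choice is the participant's. Only termination belongs to the investigator, it reaches stoppers only if non-use is read as noncompliance, and it must be reported to the monitors. Section 10.3, by calling non-use a major protocol deviation, makes that reading plausible but does not settle it.

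Nor does it follow that mITT and PP would nearly coincide, since PP also excludes inconsistent use, eligibility failures and missing measures.

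Three further objections have weight. First, the numerical effect works through replacement and a completers-only mITT: if leavers were kept in the denominator as non-successes, two stoppers would cap the result at 18/20 on either route. Second, 2.2 argues that ratings should follow adequate experience with the device, so early ratings are not equivalent to three-week ones. Third, device return is not a scheduled study visit and 5.4.1 foresees that it may fail, so an exit survey will miss some people. The option to keep the processor after Visit 2 (2.3.2) also gives participants a reason to stay. These points limit the size of the problem and the reach of the remedy. They do not supply the missing rule.

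**Conclusion.** The point holds as an unreconciled gap with a likely direction of bias. Following the rules as written can remove probable unfavourable raters from both primary analysis sets without a rating ever being sought. With 19 of 20 needed under the assumed test, the participant's choice or the site's decision for one or two people can change the primary result. Under the assumptions shown, the chance of a false pass rises from 3.7% to 8.5% at 5% stopping and to 19.3% at 10%. These figures are illustrations. They rest on an assumed stopping rate, on every stopper being an unfavourable rater, on every stopper being replaced, and on an exact binomial test that the plan does not name. If few people stop, or they stop for reasons unrelated to the design, the effect is small.

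**What to change.** 1. Reconcile 2.3.1, 5.4.1, 5.4.2 and 10.3 so that they give one account of the study status of someone who stops using the device.
2. Amend 5.4.2 so that a participant who stops or leaves early, and has not withdrawn consent to data collection, is offered the APCS at exit, at device return or at Visit 2. Record the date of and reason for stopping on the CRF.
3. Word 10.3 so that these ratings enter the mITT primary analysis, including when the person has been replaced. Flag them by length of wear, and report the result with and without short-wear ratings.

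None of this affects anyone's freedom to stop wearing the device or to withdraw consent. The cost is protocol wording, a small CRF addition and one extra presentation of the primary result. The downsides are that some ratings will follow short wear and some leavers will still be missed.

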2.3.2 KNOWN POTENTIAL BENEFITS

Advances in audio processor design may provide improved wearing comfort, usability, satisfaction, and durability with the SONNET 3 (EAS) (EAS) Audio Processor. This study will evaluate potential benefits to inform future device labeling, insurance coverage, clinical guidance, and product development for all MED-EL cochlear implant users. After completing Visit 2, study participants may choose to keep the SONNET 3 (EAS) (EAS) Audio Processor or return the SONNET 3 (EAS) (EAS) and continue using their existing audio processor.

2.2.3 ASSESSMENT OF KNOWN POTENTIAL RISKS AND BENEFITS

This study will include experienced MED-EL CI users who have worn an FDA-approved SONNET (EAS) or SONNET 2 (EAS) Audio Processor (P000025/S078 and P000025/S112, respectively) for at least 12 months. The SONNET/SONNET 2 (EAS) Audio Processors (AP) are part of the MED-EL Cochlear Implant System (P000025). The SONNET 3 (EAS) (EAS) AP is not expected to pose any greater risk of harm to participants than SONNET/SONNET 2 (EAS) APs. Advances in technology with SONNET 3 (EAS) (EAS) may provide new design features to improve wearing comfort and streamlined connectivity to improve usability. Thus, the benefits of SONNET 3 (EAS) (EAS) are expected to outweigh the residual risk in this population. Periodic advances in audio processor technology are standard practice and expected in the field of cochlear implants. This study is intended to collect clinical data on patient-reported satisfaction and performance with SONNET 3 (EAS) (EAS) before commercial availability in the United States to assist with future product launch and insurance coverage.

